## 4. STUDY POPULATION

## 4.1 Population

Tremor is the most common movement disorder and is defined as 'an involuntary rhythmic oscillation of a body part, mediated by alternating contractions of reciprocally acting . Tremors can be classified in a number of ways, based on the frequency, amplitude and affected body part. Besides, there are different neurological disorder that can cause the tremor, for example Essential Tremor, Parkinson's Disease, dystonia and Multiple Sclerosis. Finally, distinction can be made in the type of tremor: resting tremor (the tremor occurs when the limb is in rest) and action tremor (the tremor occurs during voluntary movement or when the limb is positioned against gravity). Patients that will be included in this study must be over 18 years old and must have an invalidating forearm tremor. This implies that they have difficulties in performing daily activities as scored with the ADL self-assessment questionnaire by Bain and Findley. In the present study, invalidating tremor is defined as having a minimum subscore of 30 across all upper limb items and an ADL score of at least 3 in at least one upper limb item. In case of doubt regarding in- or exclusion criteria, the judgement of the principal investigator prevails over the self-assessed judgement of the patient. The typical population in which this tremor is observed are patients diagnosed with ET, as described in the introduction. However, diagnostic criteria are not strict and there is no golden standard for this diagnosis. Therefore, misdiagnosis can occur, since the same invalidating action tremor is (although less frequently) observed in other neurological disorders, such as Parkinson's Disease, dystonia and Multiple Sclerosis.

## 4.2 Inclusion criteria

Based on comparable studies , the following inclusion criteria are defined for participants:

- Participant is at least 18 years of age.
- Willing to sign the informed consent.
- Diagnosed with Essential Tremor.
- Significant disability due to forearm tremor. A minimum subscore of 30 across all upper limb items, scored for the most affected arm/hand with the Bain and Findley ADL scale .
- A tremor severity subscore of 13 or higher in the arm/hand as measured by 7 rated TETRAS tasks. The posture and ADL tasks are assessed using the scale used to assess the upper limb tremor.
- A predominant FPS and/or WFE tremor with minor influence of SIER, EFE and FFE tremor according to the principal investigator's judgement. When no clear judgement can be formed, assessment of DOFs using TETRAS' upper limb tremor scale can be performed using the method in Appendix I.

Note: a predominant FPS and/or WFE tremor with the absence of a SIER, EFE and FFE is defined as: a rating below 1,5 in the SIER in a maximum of two rated TETRAS tasks AND below 2 in the EFE and FFE in a maximum of two rated TETRAS tasks

The amplitude of the postures and ADL tasks is rated peak-to-peak using TETRAS' upper limb tremor scale. More thorough instructions on how the tremor DOFs are assessed are included in Appendix I.

## 4.3 Exclusion criteria

- Dominant shoulder internal/external rotation tremor.
- Dominant elbow flexion/extension tremor.
- Excessive alcohol consumption, as defined in the GGZ guidelines on alcohol use .

- Previous or planned Deep Brain Stimulation (DBS) at time of study enrollment that interferes with testing.
- Previous or planned thalamotomy procedure, including stereotactic thalamotomy, gamma knife radio surgical thalamotomy, and focused ultrasound for the treatment of tremor at time of study enrollment that interferes with testing.
- Change in medications related to tremor disorder in the 30 days prior to study enrollment.
- A hand circumference smaller than 170 mm, or larger than 250 mm.
- An upper arm circumference smaller than 180 mm, or larger than 350 mm.
- Swollen, infected, inflamed areas, or skin eruptions, open wounds, or cancerous lesions
  of skin on the forearm or hand that would wear the orthosis during the clinical
  investigation.
- Peripheral neuropathy affecting the tested upper extremity (e.g. Carpal tunnel syndrome)
- The suspicion or confirmation that head tremor may cause impairment in performing ADL tasks.
- Diagnosed Parkinson's disease, this includes presence of parkinsonian features.
- Diagnosed functional tremor.
- Diagnosed physiologic tremor.
- Diagnosed cerebellar tremor.
- Diagnosed Multiple Sclerosis (MS).
- Diagnosed ataxia.
- Patients with an amputation of one or both upper extremities.
- Subjects with a restricted movement or restricted muscle function in the arm and or hand (e.g. contractures).
- Botulinum toxin injection for hand tremor within 6 months prior to study enrollment.
- Alcohol or caffeine consumption within 10 hours of study enrollment.
- Heavy physical training within 10 hours of study enrollment.
- Subjects unable to communicate with the investigator and staff due to:
  - Not mastering the Dutch language.
  - o Blindness.
  - o Deafness.
- Subjects with illiteracy.
- Pregnancy or anticipated pregnancy at time of study enrollment.
- Any health condition that in the neurologist's opinion should preclude participation in this study.

## 4.4 Sample size calculation

The first primary outcome measure, the TETRAS score, is normally distributed . The seven performed tasks are rated on a 0-4 scale of which three with halve points. When the scores are summed, the total outcome has a resolution of 3\*9 + 4\*5 = 47 steps, and can be seen as a continues outcome measure.

The second primary outcome measure, IMU measurements, is continuous and has a logarithmic relationship with respect to the TETRAS scale and is therefore lognormally distributed. After applying a logarithmic transformation, the IMU data will also be normally distributed .

Given the above characteristics of the outcome measures (see Section 2) and the crossover study design (see Section 3), the sample size has been calculated with G\*power using a two-tailed matched pair t-test.

G*Power 3.1.9.7	-	- 🗆 🗙	1		
File Edit View Tests Calculator Help					
Central and noncentral distributions Protoc	ol of power analyses				
0.3 0.2 0.1 0 -2 0 Test family Statistical test	critical t = 2.74438	6			
t tests V Means: Difference betwee	een two dependent means (matched pair	s) ~			
Type of power analysis			Fr	om differences	
A priori: Compute required sample size - gi	ven $\alpha$ , power, and effect size	~		Aean of difference	0
Input Parameters	Output Parameters			SD of difference	1
Tail(s) Two	
 
Noncentrality parameter δ
 
	3.6660606			
Determine => Effect size dz 0.800	0000 Critical t	2.7443764	Fr Fr	om group parameter	s
α err prob 0.	0125 Df	20		Mean group 1	14
Power (1-β err prob)	0.8 Total sample size	21		Mean group 2	10
	Actual power	0.8100407		SD group 1	5
				SD group 2	5
			Correlatio	n between groups	0.5
			Calculate	e Effect size dz	0.8
			Calcula	ate and transfer to m	ain window
					Close
	X-Y plot for a range of values	Calculate			

Figure 3: G\*Power calculation

Four studies, in which the effect of an active hand device on tremor amplitude is investigated, are used to estimate the effect size. Two of these studies did not use mechanical suppression, but reduced the tremor by means of nerve or muscle stimulation. More information about these studies can be found in Section 6.2 and 6.3.

- Steadi-One; a mechanical device which uses of fluids for reducing amplitude of motions . Results show those patients who improved by kinematic analysis had a 0.81-point score clinical improvement. There was a 0.57-point improvement in dynamic tasks based on the Fahn-Tolosa-Marin clinical rating scale (FTM) .
- The study of Lin et al. (2018) evaluated the CALA wrist device that used nerve stimulation to reduce hand tremor. This study showed a tremor amplitude reduction of 60% ± 8.4% (n = 23) which was significantly greater in the treatment than in the sham group .
- The Liftware Spoon, a handheld assistive device which also makes use of active cancellation of tremor, reduced the tremor amplitude with 73% ± 13% (n = 11) .
- The out-of-phase wrist device that uses electrical stimulation of antagonistic muscle of Maneski et al (2011) showed a significant reduction in tremor amplitude of 67% ± 13% (n = 7)
   .

Given the fact that the effects showed in other anti-tremor device studies were large, and the patients only benefit from a device that has a large effect on their tremor, the effect size d 0.8 was chosen .

An example calculation where the orthosis reduces 4 points (out of 28 total) on the TETRAS scale, assuming a standard deviation of 5 for both groups, generates this effect size of 0.8 (see Figure 3).

In total, 4 conditions will be compared with 2 different outcome measures; baseline vs. intervention (TETRAS), sham vs. intervention (TETRAS), baseline vs. intervention (IMU data) and sham vs. intervention (IMU data).

Taking into account a worst-case scenario of type 1 errors accumulation over the 4 testing conditions, a Bonferroni correction of alpha = 0.05/4 = 0.0125 is used.

The power value of 0.8 has been used, since this value is common practice in medical literature.

Using the above-mentioned parameters, it can be concluded that a minimum of 21 patients is needed. In order to compensate for possible drop-outs (10%), 25 patients will be included for this clinical investigation.

If the data is not normally distributed (after log compensation), unlike described in literature, the statistical analyses can also be performed by means of 4 Wilcoxon matched pair tests. This has no consequences for the sample size, since the sample size analysis in such case will result in 22 patients.

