## 2. OBJECTIVES

## 2.1 Primary Objectives

The primary objective of this clinical investigation is to assess the performance of the orthosis, divided over two co-primary objectives:

- 1. To evaluate the effect of the STIL anti-tremor orthosis on tremor *severity* reduction in Essential Tremor patients with an invalidating forearm tremor.
- 2. To evaluate the effect of the STIL anti-tremor orthosis on tremor *amplitude* reduction in Essential Tremor patients with an invalidating forearm tremor.

The co-primary objectives have two endpoints. The endpoint of the first primary objective is the assessment of the TETRAS scale by a trained neurologist(s). The expectation is that the orthosis will reduce tremor *severity* by one measure on the TETRAS scale (e.g. from severe to moderate). The endpoint of the second primary objective is achieved by measuring arm motion with an IMU sensor. The expectation is that the orthosis will reduce tremor *amplitude* by more than 60%.

Together, the primary endpoints give a comprehensive evaluation of the performance of the device.

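### Fixed Bonferroni at 0.0125 for the four primary comparisons is valid but gives up power that Holm's procedure recovers at the same family-wise 0.05

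*Protocol*

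**What the plan says.** Protocol Section 2.1 describes the primary objective as "divided over two co-primary objectives", tremor severity (TETRAS) and tremor amplitude (IMU), and adds: "Together, the primary endpoints give a comprehensive evaluation of the performance of the device".

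Section 4.4 says: "In total, 4 conditions will be compared with 2 different outcome measures". The list that follows has four comparisons: orthosis against baseline and orthosis against sham, on each outcome. To guard against accumulated type 1 error, "a Bonferroni correction of alpha = 0.05/4 = 0.0125 is used". The sample size was computed "using a two-tailed matched pair t-test", and "the effect size d 0.8 was chosen". The worked example is a 4-point TETRAS reduction, "assuming a standard deviation of 5 for both groups, generates this effect size of 0.8". The G*Power panel shows a correlation of 0.5 between conditions, alpha 0.0125, a total sample of 21 and an actual power of 0.8100. With a 10% drop-out allowance, 25 patients are to be enrolled.

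Section 9.1 names the paired t-tests and a Wilcoxon fallback. It states no alpha and no order of testing. Neither section gives a joint power or says which combination of the four results counts as success.

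**The concern.** A fixed threshold of 0.0125 for every test is the simplest way to hold the family-wise error at 0.05, but it is never more powerful than Holm. Holm starts at the same 0.0125 for the smallest p-value and relaxes the threshold after each rejection. It therefore rejects whatever Bonferroni rejects and sometimes more, with no assumption about how the tests are correlated.

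The 0.81 in the sample-size panel belongs to one comparison, and the protocol does not say so. The two endpoints are described as evaluated together and both contrasts are of interest, so a reader may take 0.81 for the power of the primary analysis as a whole. At stake are real effects with p-values between 0.0125 and 0.05 that the plan would leave undeclared although a method with the same error rate could declare them.

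**Working it through.** **Inputs from Section 4.4:** four two-sided paired t-tests; alpha 0.05/4 = 0.0125; difference 4 points; SD 5 in each condition; correlation 0.5 between conditions; minimum n 21; 25 enrolled.

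**Assumed:** dz 0.8 for all four tests (the worked example is for TETRAS only); the correlation of 0.5 and equal SDs hold for every pair of conditions; correlation between the TETRAS and IMU differences from 0 to 0.9. The protocol says the two outcomes are related but gives no figure for the last.

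**Step 1: reproduce the plan's figure.**
- SD of the difference = √(25 + 25 − 2 × 0.5 × 25) = 5, so dz = 4/5 = 0.80.
- At n=21: df 20, critical t 2.7444, noncentrality 0.8 × √21 = 3.666, power 0.8100. At n=20 power is 0.783, so 21 is the minimum. The stated result reproduces.
- At n=25 the same single-test power is 0.892.

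**Step 2: correlation between the two contrasts of one outcome.** Both share the orthosis run. With B, S and I for baseline, sham and orthosis, Cov(B−I, S−I) = Cov(B,S) − Cov(B,I) − Cov(I,S) + Var(I) = 12.5 − 12.5 − 12.5 + 25 = 12.5. Dividing by the variance of 25 gives 0.5.

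**Step 3: simulate four correlated paired t-tests** (200,000 trials per setting). Bonferroni: every p ≤ 0.0125. Holm: ordered p-values against 0.05/4, 0.05/3, 0.05/2 and 0.05, stopping at the first failure. Unadjusted: every p ≤ 0.05.

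Probability that all four are significant:

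| n | Correlation between endpoints | Bonferroni | Holm | Each at 0.05 |
|---|---|---|---|---|
| 21 | 0 | 0.485 | 0.771 | 0.789 |
| 21 | 0.5 | 0.543 | 0.792 | 0.813 |
| 21 | 0.7 | 0.577 | 0.806 | 0.828 |
| 21 | 0.9 | 0.626 | 0.821 | 0.853 |
| 25 | 0 | 0.669 | 0.885 | 0.893 |
| 25 | 0.5 | 0.707 | 0.893 | 0.903 |
| 25 | 0.7 | 0.730 | 0.898 | 0.911 |
| 25 | 0.9 | 0.764 | 0.904 | 0.923 |

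Over correlations 0 to 0.8, the range used for the conclusion, Bonferroni gives 0.49-0.60 and Holm 0.77-0.81 at n=21. At n=25 the figures are 0.67-0.74 and 0.88-0.90. A 10% loss from 25 leaves 25 × 0.9 = 22.5; at 22-23 evaluable patients, Bonferroni gives 0.54-0.70 and Holm 0.81-0.87 (correlations 0 to 0.9).

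**Step 4: power per test and chance of any success.**
- Per test, n=21: Bonferroni 0.81; Holm 0.908, 0.901 and 0.894 at correlations 0, 0.5 and 0.7.
- Per test, n=25: Bonferroni 0.89; Holm 0.959, 0.953 and 0.951 at the same correlations.
- At least one success, n=21: 0.994, 0.981 and 0.953 at correlations 0, 0.5 and 0.9, identical for both methods because the first threshold is the same.

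**Step 5: error rate.** With all four nulls true, the simulated family-wise error was 0.045 for both methods. With one, two or three nulls true, it was 0.040, 0.041 and 0.043 for Holm, against 0.013, 0.024 and 0.035 for Bonferroni. Holm stays under 0.05.

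**The case against.** The strongest reply is that nothing here is an error. Bonferroni is valid, the protocol presents it as a worst-case safeguard, and n=21 follows correctly from the stated inputs. That stands: this is an efficiency gain, not a correction. It remains worth raising because Section 4.4 itself fixes the method and the alpha rather than leaving them open.

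Several stronger readings are tempting, and the protocol does not support them.

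- *The trial has only about a 50-60% chance of success.* A reader might infer this from the co-primary label and the statement that the endpoints are evaluated together. No section requires all four comparisons to succeed. The sentence in Section 2.1 describes the endpoints and is not a decision rule, while a correction for accumulated error fits a plan in which any single success may count. If any one is enough, power is already 0.95-0.99 at n=21 and Holm adds nothing to it. The figure also applies only at the minimum of 21. The plan enrols 25, and Section 7.5 provides for new patients if the sample drops.
- *A mixed set of p-values is the likely result, and the plan could not conclude from it.* At n=21, at least one p below 0.0125 together with at least one between 0.0125 and 0.05 has probability 0.39, 0.36 and 0.32 at endpoint correlations 0, 0.5 and 0.8, less than all four below 0.0125 in each case. Each comparison would still have a clear verdict at 0.0125. What is missing is an overall success rule, and Holm does not supply one.
- *Holm costs nothing.* Bonferroni has simple matching 98.75% intervals (1 − 0.0125); Holm does not.

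It is also fair to say that the equal dz of 0.8 for the sham contrast and for log-amplitude stretches a TETRAS example, and that the correlation between endpoints is assumed.

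**Conclusion.** The point holds as a cheap improvement. The plan's multiplicity control is valid and its sample size is right, but the fixed 0.0125 forgoes power that Holm recovers at family-wise 0.05: about 0.08-0.10 per test at n=21 (0.81 to 0.89-0.91) and about 0.06 at n=25 (0.89 to about 0.95). If the sponsor hopes to claim all four effects, the difference is larger, for example 0.54 against 0.79 at n=21 with endpoint correlation 0.5. Under that setting, Bonferroni needs about 28-29 evaluable patients for 80% all-four power, and Holm 21-22.

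The figures rest on dz 0.8 for every test, correlation 0.5 between contrasts, and an assumed 0 to 0.8 between endpoints. Holm's error control and its dominance over Bonferroni rest on none of these.

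The success rule decides how much this matters. If all four comparisons must succeed, no adjustment is needed: each may be tested at 0.05, and all-four power at n=21 is 0.79-0.84, slightly above Holm.

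**What to change.** - **Section 4.4:** replace the fixed 0.0125 by Holm's procedure at family-wise 0.05, comparing the ordered p-values in turn with 0.05/4, 0.05/3, 0.05/2 and 0.05 and stopping at the first that fails. Say that 0.81 is the power of one test at 0.0125. The minimum of 21 need not change.
- **Section 9.1:** insert the same rule, since no alpha stands there now. It applies equally to p-values from the Wilcoxon fallback.
- **Same edit:** state whether success needs any one comparison, both endpoints or all four. If all four, test each at 0.05 and omit Holm.
- **Timing:** Section 3 says the study has started, and Section 7.2 says the investigator knows which device is being tested. The change should therefore be documented before any outcome analysis.

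The cost is a few sentences and a documented amendment, with no extra patients, visits or measurements. The one loss is simple matching confidence intervals; 98.75% intervals can be kept and labelled as descriptive.

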## 5. TREATMENT OF SUBJECTS

## 5.1 Investigational product/treatment

The device that will be tested in this study is the STIL anti-tremor orthosis. This non-invasive passive device uses the principle of applying external joint damping as its working principle. Two types of dampers are used to restrict high frequency involuntary motion, leaving low impact on voluntary motion, to passively suppress the forearm tremor. This will support ET patients in their daily and social activities.

A sham device is used to investigate and eliminate the influence of the weight of the STIL orthosis on tremor suppression and to validate the working principle of the dampers. The sham device used has no damping elements, but has a similar look and weight (see *IMDD chapter 1.1.i*).

## 5.2 Use of co-intervention

As written in the inclusion and exclusion criteria, patients may not have changed their medication in the 30 days prior to study entry. An implanted electrical deep brain stimulator is not allowed. Besides, patients may not consume caffeine or alcohol in the 10 hours prior to study enrolment. Caffeine is known to intensify tremor, while alcohol may suppress the tremor.

## 5.3 Escape medication

Does not apply to this study.

## 6. INVESTIGATIONAL PRODUCT

## 6.1 Name and description of investigational product

The STIL anti-tremor orthosis consists of an elbow piece and a hand piece, connected by a rigid extension element, via a total of 3 joints. The wrist and forearm joints are equipped with passive dampers which exert an additional damping to the respective joint. In this manner, high frequency involuntary movement, such as tremor, is suppressed but voluntary movement is still allowed. In this study, the beta-prototype (pre-market release version) of the orthosis will be

tested (Figure 1). The device is completely passive, and thus does not require software or electronics for its operation.

## 6.2 Summary of findings from non-clinical studies

- The study of Belda-Louis et al. (2003) identified tremor joint torques on a study of 18 patients, with different demographics and sexes. The dampers used to suppress the tremor are selected based on their findings regarding joint torque per DOF and per tremor type. The joint torque values in kinetic tremors are taken as reference point, as these involve tasks in which ET patients are most hindered. For suppression in the WFE tremor, a damper with a same damping torque was used. For the FPS tremor, a lower damping torque is used. Based on testing with healthy subject, it was found that a higher torque would obstruct voluntary motion too much. This provides the proof that tremor could theoretically be counteracted with the investigational device.
- A representative version of the investigational device has been tested in an internal feasibility study to test the safety, comfort and hygiene of the orthosis. Six healthy volunteers wore the orthosis for 8 hours, spread over 1-2 days. No severe adverse events were reported. More information on this is found in *IMDD Appendix VIII*.

## 6.3 Summary of findings from clinical studies

To date, no clinical studies have been performed with the STIL orthosis. However, clinical studies investigating the effects of both active and passive devices on tremor amplitude and severity, have been conducted in the past.

- The study of Lin et al. (2018) evaluated the CALA wrist device. This device uses nerve stimulation as a non-invasive therapy to aid in the symptomatic relief of hand tremor. Subjects were randomized to treatment or sham groups. A significant tremor reduction of 60% ± 8.4% (p = 0.02) was found in the treatment group compared to the sham group. Blinded rater scores (TETRAS) significantly improved following stimulation (1.77 ± 0.21) compared with pre-stimulation (2.77 ± 0.22) .
- The Liftware Spoon; a non-invasive handheld device using Active Cancellation of Tremor (ACT) technology to stabilize an eating utensil. The ACT system senses tremor direction and moves the spoon in the opposite direction to stabilize it. In this double-blinded study, patients performed certain tasks with and without stimulation of the device. Results showed a reduction of tremor amplitude of 73% ± 13% with stimulation of the device. Rater scores (Fahn-Tolosa-Marin rating scale) improved significantly during three tasks with stimulation (holding:  $1.00 \pm 0.76$  vs.  $0.27 \pm 0.70$ , eating:  $1.47 \pm 1.06$  vs.  $0.13 \pm 0.64$  and transferring:  $1.33 \pm 0.82$  vs.  $0.27 \pm 0.59$ ).
- Steadi-One; a mechanical device that integrates a tuned mass damper contains a non-Newtonian fluid to suppress tremors. When vibration energy is transferred to the added mass, this fluid become viscous, reducing its amplitude of motions . Results show those patients who improved by kinematic analysis had a 0.81-point score clinical improvement. There was a 0.57-point improvement in dynamic tasks based on the Fahn-Tolosa-Marin clinical rating scale (FTM) .

